## **11.3 Proportion of Subjects Recurrence-Free**

The proportion of subjects in each treatment group who are genital herpes recurrence-free at 6 months after the maintenance dose will be tabulated and compared using a chi-square test for homogeneity of proportions.

## **11.4 Time to First Genital Herpes Recurrence**

Time to the first subject-reported recurrence in the 6 month period after the maintenance dose will be estimated via Kaplan-Meier approach. The log rank test will be used to compare time to first recurrence between the GEN-003 and placebo arms.

## **11.5 Duration of Genital Herpes Recurrences**

Mean lesion outbreak duration is defined as the average number of days with lesions per outbreak for those who have lesion outbreaks (recurrences).

Mean lesion outbreak duration will be presented in a similar descriptive summary table as done for lesion rate as described above. Individual subject mean outbreak duration will be summarized by treatment arm over 6 months (Days 1 to 183) after the maintenance dose. A Wilcoxon rank sum test will be used to test the hypothesis that the median mean lesion outbreak durations are the same between treatment groups at 6 months after the maintenance dose.

## **11.6 Antiviral Medication Use**

Antiviral medications will be coded using the most current WHO Drug Dictionary and summarized by anatomical therapeutic chemical class and preferred term with results presented by treatment group. Antiviral medication use (Y/N) during the 6 months following the maintenance dose will be summarized by treatment group.

## **12 SAFETY ANALYSES**

### **12.1 Reactogenicity**

Frequency counts will be presented for systemic events and local reactions for the safety population. This will be done for events occurring within the first 7 days following the maintenance dose. Results will be presented by treatment group and maximum severity. Duration, in days, of events will also be summarized with n, median, minimum and maximum. All analyses will be done for the safety population.

Antipyretic and analgesic medications taken within 7 days after the maintenance dose will also be summarized by treatment group.

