6.1 Definitions and Descriptions of Assessments and Procedures

Serum/urine pregnancy tests – For all women

Daily electronic reporting tool – Each day subjects will report the presence or absence of genital herpes lesions and genital herpes symptoms. In addition, if genital herpes symptoms are present, subjects will also rate the severity of the symptoms using the questions from the Genital Herpes Signs and Symptoms Diary ([Appendix 5](#)). Data must be entered daily through Month 6 Visit. Each subject will receive a daily reminder if data have not been entered for that day. The investigational site will receive a weekly e-mail notification if a subject has missed any data, and the site should make contact with the subject to promote compliance. Site staff will also review the data in the tool each week and at each visit.

Genital herpes lesions – Papules, pustules, vesicles, or ulcers, including those that have crusted. Symptoms of prodrome, redness, itchiness, or post-inflammatory hyperpigmentation of re-epithelialized ulcers do not constitute the presence of lesions.

EQ-5D-5L – The subject will complete this questionnaire on each day of the genital herpes first recurrence after the maintenance dose through Month 6. A pad of paper copies of the questionnaire will be provided to each subject after the maintenance dose is administered.

Reactogenicity – Subjects will be interviewed and examined at 1 hour after the maintenance dose and the following items will be entered in the eCRF:

- Local reactions: Pain, tenderness, swelling, redness
- Systemic events: Headache, chills, fatigue, nausea, vomiting, diarrhea, muscle aches
- Oral temperature

The subjects will also record these items on a paper Diary Card for the first 7 days after the maintenance dose, and the information will be entered in the eCRF.

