#### **4.2 Safety Population**

The Safety population includes all randomized subjects who received the maintenance dose. Subjects will be analyzed according to the treatment received.

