## **5.5 Data Handling**

### **5.5.1 Method for Handling Missing Data**

No imputation of missing data will be performed. All available safety and efficacy data will be included in data listings and summaries.

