**Table 14.3.1.6: Frequency Table of All Adverse Events with ≥ 5% Occurrence by SOC, Preferred Term, and Treatment**

Safety Population

	GEN-003 60 ug/ M2 50 ug N=xx	Placebo N=xx
MedDRA SOC Preferred Term		
Total Number (%) of Subjects With AEs	x (x.x)	x (x.x)
SOC1	x (x.x)	x (x.x)
PT1	x (x.x)	x (x.x)
PT2	x (x.x)	x (x.x)
---		
SOC2		
PT1	x (x.x)	x (x.x)
PT2	x (x.x)	x (x.x)
---		
-----		
SOCn		
PT1	x (x.x)	x (x.x)
PT2	x (x.x)	x (x.x)
---		

Note: Adverse event mapping was based on the MedDRA Version xx.x thesaurus.

Note: Subjects who have the same event more than once are counted only once for the Preferred Term. Subjects who have more than one adverse event within a System Organ Class are counted only once in that System Organ Class.

Program:

Date Produced: mm/dd/yy

Programming Notes:

- Include all SOC/PT where the active treatment group has a ≥ 5% occurrence rate for that SOC/PT.

[Sponsor]

Protocol: [Protocol number]

page x of y

**Table 14.3.1.7: Summary of Local Reactions and Systemic Events Occurring Within 7 Days Postdose by Treatment and Maximum Severity**  
Safety Population

Local Reactions and Systemic Events	Grade [1]	GEN-003 60 ug/ M2 50 ug N=xx	Placebo N=xx
Any Local Reaction or Systemic Event	Any	n (x.x%)	n (x.x%)
	1	n (x.x%)	n (x.x%)
	2	n (x.x%)	n (x.x%)
	3	n (x.x%)	n (x.x%)
	4	n (x.x%)	n (x.x%)
Any Local Reaction	Any	n (x.x%)	n (x.x%)
	1	n (x.x%)	n (x.x%)
	2	n (x.x%)	n (x.x%)
	3	n (x.x%)	n (x.x%)
	4	n (x.x%)	n (x.x%)
Pain	Any	n (x.x%)	n (x.x%)
	1	n (x.x%)	n (x.x%)
	2	n (x.x%)	n (x.x%)
	3	n (x.x%)	n (x.x%)
	4	n (x.x%)	n (x.x%)
Tenderness	Any	n (x.x%)	n (x.x%)
	1	n (x.x%)	n (x.x%)
	2	n (x.x%)	n (x.x%)
	3	n (x.x%)	n (x.x%)
	4	n (x.x%)	n (x.x%)
Swelling	Any	n (x.x%)	n (x.x%)
	1	n (x.x%)	n (x.x%)
	2	n (x.x%)	n (x.x%)
	3	n (x.x%)	n (x.x%)
	4	n (x.x%)	n (x.x%)
Swelling (mm)	Any	n (x.x%)	n (x.x%)

Local Reactions and Systemic Events	Grade [1]	GEN-003 60 ug/ M2 50 ug N=xx	Placebo N=xx
	1	n (x.x%)	n (x.x%)
	2	n (x.x%)	n (x.x%)
	3	n (x.x%)	n (x.x%)
	4	n (x.x%)	n (x.x%)
	Any	n (x.x%)	n (x.x%)
	1	n (x.x%)	n (x.x%)
	2	n (x.x%)	n (x.x%)
	3	n (x.x%)	n (x.x%)
	4	n (x.x%)	n (x.x%)
Redness (mm)			
Any Systemic Event	ETC	n (x.x%)	n (x.x%)
Fever	ETC	n (x.x%)	n (x.x%)
Headache	ETC	n (x.x%)	n (x.x%)
Chills	ETC	n (x.x%)	n (x.x%)
Fatigue	ETC	n (x.x%)	n (x.x%)
Nausea	ETC	n (x.x%)	n (x.x%)
Diarrhea	ETC	n (x.x%)	n (x.x%)
Vomiting	ETC	n (x.x%)	n (x.x%)
Muscle aches	ETC	n (x.x%)	n (x.x%)
Any Local Reaction or Systemic Event		n (x.x%)	n (x.x%)

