Any Local Reaction		n (x.x%)	n (x.x%)
Pain		n (x.x%)	n (x.x%)
ETC			

Program:

Date Produced: mm/dd/yy

Programming Notes:

- Information comes from the Diary Card
- If a subject has multiple of the same events, take the maximum severity.
- During the 7 day period after the (Days 1-7) a subject should only be counted one time. If a subject has a sign/symptom at least once during that 7 day interval the subject is counted for that sign/symptom.
- Watch page breaks. Please try and keep all the grades together for a sign/symptom.
- Do not include Grade=0 as Grades of 0 imply "None" or no event.
- Fever is based on Temperature (F) which is collected on the Diary Card. See Appendix 2 in the protocol for grade definitions. Grade 1 = 100.4-101.1; Grade 2 = 101.2-102.0; Grade 3 = 102.1-104; Grade 4 >104.

- For Redness (mm) and Swelling (mm), see also Appendix 2 in the protocol. For both redness and swelling: Grade 1 = 2.5-5 cm; Grade 2 = 5.1-10 cm; Grade 3 = >10cm; Grade 4 is Necrosis or exfoliative dermatitis, which we won't be able to determine and will be handled separately as an AE.

[Sponsor]

Protocol: [Protocol number]

page x of y

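### As drawn, the reactogenicity table shows a dosed subject without Diary Card data as having no reaction, and does not report how many subjects supplied data

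*SAP*

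**What the plan says.** SAP 12.1 opens with "Frequency counts will be presented for systemic events and local reactions for the safety population", limited to the first 7 days after the dose. SAP 4.2 defines that set: "The Safety population includes all randomized subjects who received the maintenance dose". It sets no condition about diary data.

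The display is Table 14.3.1.7, titled "Summary of Local Reactions and Systemic Events Occurring Within 7 Days Postdose by Treatment and Maximum Severity". It is headed Safety Population, with N per arm and n (x.x%) in each cell. Its programming notes say "Information comes from the Diary Card" and "If a subject has a sign/symptom at least once during that 7 day interval the subject is counted for that sign/symptom". They also tell the programmer to leave out grade 0. There is no row for subjects with card data, none for subjects without, and no sentence on a lost, blank or partly completed card. The general rule in SAP 5.5.1 is "No imputation of missing data will be performed".

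Protocol 6.1 describes two collections. In the clinic, "Subjects will be interviewed and examined at 1 hour after the maintenance dose and the following items will be entered in the eCRF". At home, "The subjects will also record these items on a paper Diary Card for the first 7 days after the maintenance dose". Listings 16.2.7.1 and 16.2.7.2, both labelled as Diary Card listings, include a Day 1 (1hr) row. The SAP does not say whether that 1-hour record feeds Table 14.3.1.7.

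**The concern.** Because the shell leaves out grade 0 and has no missing category, a subject who recorded no symptoms and a subject who recorded nothing look the same: both are in N and neither is in n. In effect a missing card is read as no reaction, and the table does not say so.

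This looks like an omission, not a choice, because the SAP is explicit elsewhere. For the lesion diary (SAP 11.1) it says when a missing entry counts as a no. For recurrence-free status (Table 14.2.5.1) it prints an Unknown row and leaves it out of the test. For the electronic diary it plans a compliance table (SAP 10, Table 14.2.1). The paper card has none of these.

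Reactogenicity is the first safety endpoint listed in Protocol 2.2.3. The adverse event tables give little backup, since Protocol 6.1 keeps Diary Card events off the AE form unless they meet SAE criteria. Incomplete cards are also possible by design. The card is reviewed at the Day 8 visit, whose window of ±3 days allows a visit on Day 5, before the 7 days are over.

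**Working it through.** The plan states no reactogenicity rate or expected card return for this trial, so there is no figure to reproduce. The check is how the shell behaves when cards are missing.

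**Inputs**
- Arm size: up to 90 subjects (Protocol synopsis) randomized 1:1, so 90 / 2 = 45 per arm.
- Illustrative rates: Grade 3 local or systemic events of 51.2% (60 µg/50 µg group) and 13.6% (placebo), from Protocol 1.5.5. These are rates within 7 days of any of three doses. They are not predictions for one dose.
- Share of dosed subjects with no usable card, m: not in the documents. Assumed range 0% to 20%.

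**Formula.** If missing cards are unrelated to reaction and the card is the only source, then printed rate = true rate × (1 − m).

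**Lost cards in an arm of 45, true rate 51.2%**
- 1 card: 51.2 × 44/45 = 50.1%
- 2 cards: 51.2 × 43/45 = 48.9%
- 5 cards: 51.2 × 40/45 = 45.5%

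**Same share missing in both arms**

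| m | Active | Placebo | Difference (points) |
|---|---|---|---|
| 0% | 51.2% | 13.6% | 37.6 |
| 5% | 48.6% | 12.9% | 35.7 |
| 10% | 46.1% | 12.2% | 33.8 |
| 20% | 41.0% | 10.9% | 30.1 |

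The ratio of the two rates stays at 51.2 / 13.6 = 3.76 throughout.

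**10% missing in one arm only**
- Active only: 46.1 − 13.6 = 32.5 points, ratio 3.39.
- Placebo only: 51.2 − 12.2 = 39.0 points, ratio 4.18.

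**If the 1-hour record also feeds the table.** Suppose it catches a share s of the reactions of subjects without a card. Then printed rate = true rate × (1 − m + m × s). With m = 10%:
- s = 25%: 51.2 × 0.925 = 47.4%
- s = 50%: 51.2 × 0.95 = 48.6%

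This offsets part of the loss but not all of it.

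**Side check on the parent study.** Using the group sizes in Protocol 1.5.5, 22/43 = 51.2% and 6/44 = 13.6%. The published rates therefore fit a denominator of all subjects in the group. This does not show whether any card was missing there, and 21/41 also rounds to 51.2%.

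**The case against.** The strongest reply has five parts.

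1. **The denominator is inferred.** No sentence in the SAP sets it, and the line in SAP 12.1 speaks of frequency counts. This stands as a caution: a reader should not say the SAP prescribes an all-dosed denominator. But the population statement, the N in the header and the n (x.x%) cells make it the natural reading, and nothing points to another.

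2. **The card is not the only collection.** The same items are assessed at 1 hour and entered in the eCRF. This stands. A reader might infer that a lost card leaves no reactogenicity data at all, and the documents do not support that. It also bears on the remedy: if a 1-hour record were enough to enter the denominator, nearly every dosed subject would qualify and nothing would change.

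3. **Losses should be few.** Subjects bring the card to the Day 8 visit, where it is reviewed, and entrants had at least 80% electronic reporting in GEN-003-003. This makes heavy loss less likely but does not make the table show it. The by-subject listings would reveal gaps, so differential loss would not be wholly hidden; the summary table would hide it.

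4. **An all-dosed percentage imputes nothing and keeps comparability with earlier studies.** Partly right. Dividing observed events by subjects exposed is a common layout, also used in the AE tables, so a direct contradiction of SAP 5.5.1 is too strong a reading. Comparability is a reason to keep that percentage as a second display.

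5. **The stakes are low.** The table is descriptive and untested, and the Amendment 2 summary says development of GEN-003 has stopped. This stands and limits the weight of the point.

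**Conclusion.** The point holds in a limited form. As drawn, Table 14.3.1.7 displays a dosed subject with no usable card as a non-reactor and does not report how many subjects supplied data, so the printed rates can be understated.

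The size depends on a return rate that the documents do not give. On a 51.2% rate the loss is about 1 point for one lost card in 45 and about 5 points at 10% missing. With full return it is zero. These figures assume that missing cards are unrelated to reaction, that the 1-hour record does not feed the table, and that an any-of-three-dose rate can stand in for a single dose.

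A reader might go further and conclude that the rates will be understated, or that the difference between arms will be biased downward. The documents support neither. Understatement arises only if cards are missing. The difference shrinks when the same share is missing in both arms, but it can move either way when the shares differ.

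This is a minor improvement to a descriptive safety table. The efficacy analyses are not affected.

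**What to change.** In SAP 12.1 and the shell of Table 14.3.1.7:

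- Base each percentage on Safety subjects with at least one Diary Card entry for that item in the 7-day window after leaving the clinic. For the Any rows, require at least one solicited item.
- Print that n per arm, and add a row for dosed subjects with no Diary Card data.
- Show the 1-hour eCRF assessment separately, so that a 1-hour record alone does not place a subject in the 7-day denominator.
- If wanted, keep the all-dosed percentage as a secondary display for comparison with earlier studies.

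Two limits remain. A partly completed card is still judged only on the days recorded. If missing cards are related to reaction, the new denominator does not remove the bias; the printed counts at least let the reader judge it.

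The cost is a few lines of SAP and shell wording and trivial programming. No new data are needed. If any cards are missing, the reported rates will usually be somewhat higher than under the current shell.

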### **12.2 Adverse Events**

All AEs will be coded using the MedDRA coding system. Frequency tables will be presented by treatment group for all AEs by SOC and PT. Frequency tables will be produced for AEs leading to discontinuation of dosing, by severity, by causality, for most common ( $\geq 5\%$  in any group) AEs, SAEs, MAAEs, and AESIs. Subject listings of all AEs by study day will also be provided.

In all displays, AEs will be displayed by MedDRA SOC and PT, with subjects who have the same AE counted only once for that event and with subjects who have more than 1 AE within a SOC counted only once in that SOC.

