6.3 Follow-up Period

6.3.1 Follow-up Telephone Calls

Follow-up telephone calls will be made at each of the following time points:

- Month 2 (Day 57 ± 7 days)
- Month 4 (Day 113 ± 7 days)
- Month 8 (Day 225 ± 14 days)
- Month 10 (Day 281 ± 14 days)

The following procedures will be performed:

- Review of daily reporting tool data (Month 4 only)
- Assessment of SAEs, AESIs, and MAAEs
- Assessment of antiviral medication through Month 6

The subject will be reminded to continue use of the daily electronic reporting tool.

6.3.2 *Month 3 (Day 85 ± 7 days) and Month 6 (Day Day 169 ± 14 days) – Clinic Visits*

The following procedures will be performed:

- Review of daily electronic reporting tool data
- Collection of completed EQ-5D-5L questionnaires, if completed
- Assessment of SAEs, AESIs, and MAAEs
- Assessment of antiviral medication

6.3.3 *Month 9 (Day 253 ± 14 days) and Month 12 (Day 337 ± 14 days) – Clinic Visits*

The following procedures will be performed:

- Assessment of SAEs, AESIs, and MAAEs

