7.1 Reporting Responsibilities

All AEs (including SAEs, AESIs, and MAAEs) will be recorded from the maintenance dose to Day 29/Month 1. After Day 29/Month 1 to the end of study, only SAEs, AESIs, and MAAEs will be recorded. It is the responsibility of the Investigator or Subinvestigator(s) to perform periodic assessment of AEs. Data describing AEs will be entered in the subject's medical record and eCRF, and as appropriate, an SAE/AESI report form. SAEs and AESIs will be reported to the Sponsor as described in Section 7.6.

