## 2 STUDY OVERVIEW

This study is a randomized, double-blind, placebo-controlled clinical trial of GEN-003 in subjects who have received previous doses of GEN-003. Subjects who completed Study GEN-003-003 and received all 3 doses, reported data in daily electronic reporting period on at least 80% of days, and had no important protocol deviation in that trial were offered enrollment in this study. Subjects who met all inclusion and no exclusion criteria and provided written informed consent for this study were randomized within 11 to 18 months after the last active GEN-003 dose in a 1:1 ratio to receive 1 intramuscular (IM) dose (the maintenance dose) of GEN-003 or placebo. Randomization was stratified on the basis of the GEN-003 dose received by the subject in Study GEN-003-003.

Subjects were to use a daily electronic tool for reporting the presence or absence of genital herpes lesions and severity of genital herpes symptoms from Day 1 until the Month 6 visit.

Subjects were to complete the EuroQol – 5 Domains – 5 Levels (EQ-5D-5L) questionnaire on each day of the first recurrence after the maintenance dose through Month 6.

Local reactions and systemic events were to be recorded for the first 7 days after the maintenance dose on a paper Diary Card; if any event was ongoing after Day 8, it was to be followed until resolution. All adverse events (AEs) and concomitant medications were to be recorded from Day 1 to Day 29/Month 1. After Day 29/Month 1 to the end of the study, only serious AEs (SAEs), AEs of special interest (AESIs), medically attended AEs (MAAEs), antiviral medications, and vaccines were to be recorded. All AEs were to be graded in accordance with the Toxicity Grading Scale for Healthy Adult and Adolescent Volunteers Enrolled in Preventive Vaccine Clinical Trials from Grade 1 (mild) to Grade 4 (life-threatening).

From Month 2 to Month 6, the investigational site was to contact each subject monthly by telephone or site visit for review of daily electronic reporting tool data and assessment of SAEs, AESIs, and antiviral medication use (through Month 6).

A Data Monitoring Committee (DMC) was to review safety data at intervals of a minimum of 3 months until all subjects have completed the GEN-003/placebo dosing period. Any additional meetings and the specific safety monitoring plan were to be detailed in the DMC charter.

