**List of Statistical Tables for GEN-003-005**

Table No.	Table Title	Analysis Population	IA
14.1.1	Number and Percentage of Enrolled Subjects by Site and Treatment Group	Safety	
14.1.2	Demographic and Baseline Characteristics by Treatment Group	Safety	x
14.1.3	Summary of Analysis Populations by Treatment Group		
14.1.4	Subject Disposition by Treatment Group	Safety	
14.1.5	Frequency of Medical History Events by Treatment Group	Safety	
14.1.6	Prior Medications by Treatment Group	Safety	
14.1.7	Concomitant Medications by Treatment Group	Safety	
14.1.8	Summary of Antiviral Medications Taken During the Study by Treatment Group, Drug Class and Preferred Term	Safety	
14.2.1	Summary Statistics for Electronic Diary Compliance After Maintenance Dose by Treatment Group	mITT	
14.2.2.1	Descriptive Summary of Overall Lesion Rates by Treatment Group and Observation Period	mITT	x
14.2.2.2	Descriptive Summary of Overall Lesion Rates by Treatment Group and Observation Period	PP	
14.2.3.1	Descriptive Summary of Individual Subject Lesion Rates by Treatment Group and Observation Period	mITT	x
14.2.3.2	Descriptive Summary of Individual Subject Lesion Rates by Treatment Group and Observation Period	PP	

Table No.	Table Title	Analysis Population	IA
14.2.4.1	Frequency of Recurrences at 6 Months After Maintenance Dose by Treatment Group	mITT	x
14.2.4.2	Frequency of Recurrences at 6 Months After Maintenance Dose by Treatment Group	PP	
14.2.5.1	Proportion of Subjects Who Are Recurrence Free at 6 Months After Maintenance Dose	mITT	x
14.2.5.2	Proportion of Subjects Who Are Recurrence Free at 6 Months After Maintenance Dose	PP	
14.2.6.1	Time to First Recurrence After Maintenance Dose	mITT	x
14.2.6.2	Time to First Recurrence After Maintenance Dose	PP	
14.2.7.1	Descriptive Summary and Analysis of Mean Lesion Outbreak Duration Over 6 Months After Maintenance Dose	mITT	x
14.2.7.2	Descriptive Summary and Analysis of Mean Lesion Outbreak Duration Over 6 Months After Maintenance Dose	PP	
14.2.8.1	Summary of Antiviral Medication Use After Maintenance Dose	mITT	
14.2.8.2	Summary of Antiviral Medication Use After Maintenance Dose	PP	
14.3.1.1	Frequency Table of All Adverse Events by SOC, Preferred Term, and Treatment	Safety	
14.3.1.2	Frequency Table of All Adverse Events by SOC, Preferred Term, Treatment, and Severity	Safety	
14.3.1.3	Frequency Table of All Adverse Events by SOC, Preferred Term, Treatment, and Causality	Safety	

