**Table 14.1.8: Summary of Antiviral Medications Taken During the Study by Treatment Group, Drug Class and Preferred Term**

Safety Population  
Day 1 to Month 6

Preferred Term	GEN-003 60 ug/ M2 50 ug N=xx	Placebo N=xx
Any Antiviral Medication	n (x.x%)	n (x.x%)
Preferred Term 1	n (x.x%)	n (x.x%)
Preferred Term 2	n (x.x%)	n (x.x%)
Preferred Term 3	n (x.x%)	n (x.x%)
etc.		

Program:

Date Produced: mm/dd/yy

Programming Notes:

- Antiviral medications are defined as medications with an ATC2 Class of 'ANTIVIRALS FOR SYSTEMIC USE'

[Sponsor]

Protocol: [Protocol number]

page x of y

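### The all-AE tables set no onset window, so they combine 28 days of full AE capture with about 308 days of selective capture, and no table shows unsolicited AEs by arm for Day 1 to 29

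*SAP*

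**What the plan says.** Protocol 7.1 sets two recording rules. First, "All AEs (including SAEs, AESIs, and MAAEs) will be recorded from the maintenance dose to Day 29/Month 1". Then, "After Day 29/Month 1 to the end of study, only SAEs, AESIs, and MAAEs will be recorded". SAP section 2 repeats the first rule ("All adverse events (AEs) and concomitant medications were to be recorded from Day 1 to Day 29/Month 1") and the narrowing after Day 29. Protocol 6.3.3 places the last visit, Month 12, at Day 337 with a window of 14 days either side.

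SAP 12.2 plans the analysis without carrying that change of rule forward: "Frequency tables will be presented by treatment group for all AEs by SOC and PT". Table 14.3.1.1 is titled "Frequency Table of All Adverse Events by SOC, Preferred Term, and Treatment". Its shell names no observation period in the title, the notes or the programming notes. The same holds for Tables 14.3.1.2 (severity), 14.3.1.3 (causality) and 14.3.1.6 (terms at 5% or more).

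Elsewhere the SAP does state a period. The shell for Table 14.1.8 carries the line "Day 1 to Month 6", and for reactogenicity SAP 12.1 says "This will be done for events occurring within the first 7 days following the maintenance dose".

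**The concern.** The meaning of a recorded AE changes at Day 29, but the main AE tables give one count per subject across the whole follow-up. A mild, unattended illness counts in Month 1 and is not captured in Month 3. A medically attended illness counts at any time. Read literally, the headline row mixes the two rules without telling the reader.

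The safety objective compares the tolerability of one dose with placebo. Protocol 6.1 keeps Diary Card events off the AE form unless they are serious, so the AE tables are the main summary of unsolicited events. Protocol 10.9.2 plans no formal testing of AEs, so readers will judge them from the displayed percentages, with at most about 45 subjects per arm (up to 90, randomized 1:1). If unrelated late events add to both arms, a real early difference looks smaller in those rows.

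**Working it through.** The documents give no expected AE rate, so there is no planned figure to reproduce. The window lengths come from the documents. The event rates below are assumptions.

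**Length of each period**

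- Full capture (Protocol 7.1): 29 − 1 = 28 days.
- Selective capture (Protocol 7.1 and 6.3.3): 337 − 29 = 308 days. With the visit window this is 323 − 29 = 294 to 351 − 29 = 322 days.
- Share of follow-up under selective capture: 308 / 336 = 92%. The ratio of the two periods is 308 / 28 = 11.

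**Effect of pooling on the any-AE row**

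Let p be the risk of any AE in Day 1 to 29 in a given arm. Let q be the risk of at least one SAE, AESI or MAAE after Day 29. Assume q is equal in both arms and independent of p. Then:

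- pooled risk = 1 − (1 − p)(1 − q)
- pooled difference = (p₁ − p₀)(1 − q)

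With assumed early risks of 30% and 15% (difference 15 points, ratio 2.0):

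| q | GEN-003 | Placebo | Difference | Ratio |
|---|---|---|---|---|
| 15% | 1 − 0.70 × 0.85 = 40.5% | 1 − 0.85 × 0.85 = 27.75% | 12.75 points | 1.46 |
| 30% | 1 − 0.70 × 0.70 = 51.0% | 1 − 0.85 × 0.70 = 40.5% | 10.5 points | 1.26 |
| 45% | 1 − 0.70 × 0.55 = 61.5% | 1 − 0.85 × 0.55 = 53.25% | 8.25 points | 1.15 |

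**Single preferred terms**

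For an assumed 8% versus 2% early (6.0 points, ratio 4.0), a late background of 2% to 10% lowers the difference only to between 5.9 and 5.4 points. The ratio falls to between 2.5 and 1.5.

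**When late events differ by arm**

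Take early risks of 40% and 20%, and late risks of 30% and 20%. The pooled risks are 1 − 0.60 × 0.70 = 58% and 1 − 0.80 × 0.80 = 36%. The difference is 22 points, against 20 points early. Here pooling does not dilute.

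**Whether another planned output fills the gap**

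- Tables 14.3.1.7 and 14.3.1.8 cover solicited reactions only.
- Tables 14.3.1.5, 14.3.2.1 and 14.3.2.2 cover AESIs, SAEs and MAAEs, and omit other unsolicited AEs.
- Table 14.3.1.3 splits by causality but not by onset.
- Listing 16.2.7.3 shows the start date and study day of each AE but gives no incidence by arm.

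No planned table gives unsolicited AEs by arm for the only period in which all of them are recorded.

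**The case against.** The case for leaving the tables alone has several sound parts.

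- **The percentage has a meaning.** A reader might infer that it has none. It is the share of subjects with any recorded AE. The recording rule is written in both documents and is the same in both randomized arms, so the change at Day 29 does not by itself bias the comparison. What is missing is a period label and a display by period.
- **Dilution is conditional.** A reader might infer that a vaccine-related difference is bound to be diluted. That requires late events that are unrelated to vaccine, and its size depends on a rate the documents do not give. As shown above, the difference can also grow.
- **Solicited reactions are not affected.** They have their own tables over 7 days.
- **The causality table is partly protected.** Protocol 7.2.5 describes an unlikely relationship as one with no temporal association with the product. Unrelated late events should therefore fall mostly in the Unlikely panel, leaving the Likely panel largely undiluted.
- **Not every doctor visit counts.** Protocol 7.2.2 requires an AE and leaves out routine health care visits.
- **Cutting the four tables off at Day 29 would lose something.** Protocol 10.9.2 requires SAEs, AESIs and MAAEs to be summarized by severity as well as frequency. Tables 14.3.1.5, 14.3.2.1 and 14.3.2.2 have no severity or causality breakdown, so late events of these kinds would keep that detail only in listings.

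All of this stands. It limits the consequence and rules out a simple cutoff. It does not supply the missing Day 1 to 29 table.

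**Conclusion.** The point holds as one of presentation and labelling. The four tables combine 28 days of full capture with about 308 days (294 to 322) of selective capture and do not say so.

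The possible loss of contrast is in the any-AE row. Under equal and independent late risk, the difference shrinks by (1 − q): by 15%, 30% or 45% at q = 15%, 30% or 45%. Those values of q, and the 30% versus 15% early rates behind the ratios of 1.46, 1.26 and 1.15, are assumptions. For single terms the loss is small on the difference scale but visible on the ratio scale. AEs are summarized descriptively, and onset dates are available in the listings. This is a cheap improvement and does not undermine the safety analysis.

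**What to change.** Present Tables 14.3.1.1, 14.3.1.2, 14.3.1.3 and 14.3.1.6 by onset period and state the period in each title. Make all unsolicited AEs from the maintenance dose through the Day 29/Month 1 visit the main display. Define the cut point in relation to that visit's window of 3 days either side (Protocol 6.2.3).

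Keep the whole-study SAE, AESI and MAAE tables. Keep a severity and causality tabulation for events after Day 29, so that Protocol 10.9.2 is still met.

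In the same edit, reconcile the 5% rule. SAP 12.2 applies it to either group, while the programming note to Table 14.3.1.6 applies it to the active group only.

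The cost is SAP wording, a filter on onset dates already collected, a few extra table panels, and smaller counts per panel. No new data are needed.
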